### 6.3 Appendix 3: Toxicity Grading Scale Tables

The toxicity grading scales for clinical and laboratory abnormalities are presented in [Table 6-3](#) and [Table 6-4](#), respectively. Note that for laboratory abnormalities, grading only occurs if the values reside outside of the normal values established by the clinical laboratory. For study-specific laboratory normal ranges and associated toxicity grades, refer to the laboratory manual.

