#### **3.5.7.4 Assessment of Severity**

The severity (or intensity) of an AE refers to the extent to which it affects the subject's daily activities and will be classified as mild (Grade 1), moderate (Grade 2), severe (Grade 3), or potentially life threatening (Grade 4) using the following criteria:

- Mild (Grade 1): These events do not interfere with the subject's daily activities.
- Moderate (Grade 2): These events cause some interference with the subject's daily activities but do not require medical intervention.
- Severe (Grade 3): These events prevent the subject's daily activity and require medical intervention.
- Life threatening (Grade 4): These events require an emergency room visit or hospitalization.

Changes in the severity of an AE should be documented to allow an assessment of the duration of the event at each level of intensity to be performed. An AE characterized as intermittent requires documentation of onset and duration of each episode.

The Toxicity Grading Scale for Healthy Adult and Adolescent Volunteers Enrolled in Preventative Vaccine Clinical Trials ([CBER 2007](#)) will be used to categorize solicited

reactogenicity, safety laboratory test results, and vital sign measurements observed during this study. Specific criteria for clinical and laboratory abnormalities are presented in [Table 6-3](#) and [Table 6-4](#), respectively, and will be graded if outside of the reference range for the laboratory utilized. Of note, the laboratory test value itself may not be the AE classification. Each AE will be classified by its most specific term (eg, renal insufficiency, bronchitis) and supporting evidence (eg, laboratory test value, x-ray) will not be classified as an AE per se.

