Should safety laboratory testing result in a Grade 2 or higher toxicity, repeat testing must occur within the next 10 days; this may include an unscheduled visit. Should the subject's laboratory value not return to baseline then periodic testing may be needed until the abnormality is deemed to be associated with a new stable AE or determined to be not clinically significant by the investigator.

Those values that fall within the normal range of the laboratory will automatically be classified as normal. All values that have a toxicity of Grade 1 or higher will also be evaluated by the investigator and classified as “abnormal clinically significant (CS)”, or “abnormal not clinically significant (NCS)”. Investigators should use their clinical judgment when considering the clinical significance of any abnormal laboratory findings. All laboratory test values with a toxicity of Grade 3 or higher will be entered as AEs. Any additional laboratory test value that is determined to be clinically significant will also be recorded as an AE, should that be considered the primary diagnosis. In such instances, the abnormal value and grade will be documented on the AE page of the eCRF. The investigator will continue to monitor the subject with additional assessments until the values have reached the reference range or the values at Screening or until the investigator determines that follow-up is no longer medically necessary. The only exception to this rule would be a laboratory test value that is associated with an identified ongoing AE where that event would be the classifying AE.

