Source: Guidance for industry – Toxicity grading scale for healthy adult and adolescent volunteers enrolled in preventative vaccine clinical trials; Tables for laboratory abnormalities (CBER 2007).

Hematology *	Mild (Grade 1)	Moderate (Grade 2)	Severe (Grade 3)	Potentially Life Threatening (Grade 4)
Hemoglobin (female) (g/dL)	11.0 – 12.0	9.5 – 10.9	8.0 – 9.4	< 8.0
Hemoglobin (female) change from Baseline value (g/dL)	Any decrease – 1.5	1.6 – 2.0	2.1 – 5.0	> 5.0
Hemoglobin (male) (g/dL)	12.5 – 13.5	10.5 – 12.4	8.5 – 10.4	< 8.5
Hemoglobin (male) change from Baseline value (g/dL)	Any decrease – 1.5	1.6 – 2.0	2.1 – 5.0	> 5.0
WBC increase (cell/mm  )	10 800 – 15 000	15 001 – 20 000	20 001 – 25 000	> 25 000
WBC decrease (cell/mm  )	2500 – 3500	1500 – 2499	1000 – 1499	< 1000
Lymphocytes decrease (cell/mm  )	750 – 1000	500 – 749	250 – 499	< 250
Neutrophils decrease (cell/mm  )	1500 – 2000	1000 – 1499	500 – 999	< 500
Eosinophils (cell/mm  )	650 – 1500	1501 – 5000	> 5000	Hypereosinophilic
Platelets decreased (cell/mm  )	125 000 – 140 000	100 000 – 124 000	25 000 – 99 000	< 25 000
PT; increase by factor	1.0 – 1.10 × ULN	1.11 – 1.20 × ULN	1.21 – 1.25 × ULN	> 1.25 × ULN
PTT; increase by factor	1.0 – 1.2 × ULN	1.21 – 1.4 × ULN	1.41 – 1.5 × ULN	> 1.5 × ULN

Abbreviations: PT, prothrombin time; PTT, partial thromboplastin time; ULN, upper limit of normal; WBC, white blood cell.

\* The laboratory values provided in the tables serve as guidelines and are dependent upon institutional normal parameters. Institutional normal reference ranges should be provided to demonstrate that they are appropriate.

Source: Guidance for industry – Toxicity grading scale for healthy adult and adolescent volunteers enrolled in preventative vaccine clinical trials; Tables for laboratory abnormalities (CBER 2007).

Urine *	Mild (Grade 1)	Moderate (Grade 2)	Severe (Grade 3)	Potentially Life Threatening (Grade 4)
Protein	Trace	1+	2+	Hospitalization or dialysis
Glucose	Trace	1+	2+	Hospitalization for hyperglycemia
Blood (microscopic) – red blood cells per high power field (rbc/hpf)	1 – 10	11 – 50	> 50 and/or gross blood	Hospitalization or packed red blood cells transfusion

\* The laboratory values provided in the tables serve as guidelines and are dependent upon institutional normal parameters. Institutional normal reference ranges should be provided to demonstrate that they are appropriate.

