clinically significant (NCS).” Investigators should use their clinical judgment when considering the clinical significance of any abnormal laboratory findings. All laboratory test values with a toxicity score of Grade 3 or greater will be entered as AEs. Any additional laboratory test value that is determined to be clinically significant will also be recorded as an AE, should that be considered the primary diagnosis. In such instances, the abnormal value and grade will be documented on the AE page of the eCRF. The investigator will continue to monitor the subject with additional assessments until the values have reached the reference range or the values at Screening or until the investigator determines that follow-up is no longer medically necessary. The only exception to this rule would be a laboratory test value that is associated with an identified ongoing AE where that event would be the classifying AE.

All laboratory test results will be presented in the data listings. The results that are outside the reference ranges will be flagged in the data listings. The abnormalities meeting the toxicity grading criteria (Grade 2 or higher) in any safety laboratory will be listed separately. If a subject has a laboratory test with Grade 2 or higher abnormality at any post vaccination visit, then all results for that subject and laboratory test will be presented in the listing.

For hematology, serum chemistry, coagulation, and numeric urinalysis test results, the observed values and changes from Baseline on Days 7, 17, 28 after each vaccination and for sentinel safety subjects also on Day 21 post first vaccination will be summarized by treatment groups as defined in Section 5. These laboratory tests will also be summarized by the toxicity grades.

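### Laboratory values are graded only outside the normal range, so a Grade 3-sized hemoglobin fall that stays in range gets no grade; separately, an out-of-range hemoglobin can carry two grades with no precedence rule

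*Protocol*

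**What the plan says.** Three places in the protocol govern when a laboratory result is graded.

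- Appendix 3 (section 6.3) states that "for laboratory abnormalities, grading only occurs if the values reside outside of the normal values established by the clinical laboratory". Its next sentence sends the reader to the laboratory manual for study-specific ranges and grades.
- Section 3.5.7.4 says that the criteria of Tables 6-3 and 6-4 "will be graded if outside of the reference range for the laboratory utilized". It does not say that this is the only case.
- Section 3.5.8 says "Those values that fall within the normal range of the laboratory will automatically be classified as normal".

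Table 6-4 grades hemoglobin in two ways for each sex. One row uses the value itself (for men, "Hemoglobin (male) (g/dL"). The other uses the fall from baseline ("Hemoglobin (male) change from Baseline value (g/dL" and "Hemoglobin (female) change from Baseline value (g/dL"). The change rows carry no condition about the normal range.

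SAP 9.2 summarizes laboratory tests by toxicity grade and gives a separate listing of results at Grade 2 or higher. It also repeats the protocol's rule on adverse events: "All laboratory test values with a toxicity score of Grade 3 or greater will be entered as AEs". It does not say which hemoglobin grade it means.

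**The concern.** A fall from baseline and a position relative to a population range are different measures. A subject who starts high can lose a substantial amount of hemoglobin and still finish inside the range. If the range condition is applied to the change rows, such a result has no grade, although its size matches a Grade 3 band in the protocol's own table. If the value leaves the range, two rows apply and can give different grades.

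Toxicity-graded laboratory results are among the primary safety endpoints (Protocol 3.6.1, SAP 4.2). Under Protocol 3.5.8, grade also decides repeat testing (Grade 2 or higher) and adverse event entry (Grade 3 or higher). It feeds the laboratory pause criterion in Protocol 3.4.2.2 and the laboratory toxicity scoring that the Safety Monitoring Committee reviews before escalation (Protocol 3.4.2.1). With 15 vaccine recipients per dose level, the classification of one or two results can alter how a dose group looks.

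**Working it through.** The plan states no figure for this point, so there is none to reproduce. The check applies the grading rules to hemoglobin values.

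**Inputs from Table 6-4 (g/dL)**

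| Row | Grade 1 | Grade 2 | Grade 3 | Grade 4 |
|---|---|---|---|---|
| Men, value | 12.5-13.5 | 10.5-12.4 | 8.5-10.4 | below 8.5 |
| Women, value | 11.0-12.0 | 9.5-10.9 | 8.0-9.4 | below 8.0 |
| Either sex, fall | up to 1.5 | 1.6-2.0 | 2.1-5.0 | above 5.0 |

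**Assumed input.** The documents leave the lower limit of normal (LLN) to the laboratory. I take it to lie near the top of the Grade 1 value band and vary it: 13.0 to 14.0 for men, 11.5 to 12.5 for women.

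**Step 1: when does a fall stay in range?** A fall d from baseline B ends in range if B - d ≥ LLN, that is, B ≥ LLN + d.

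- Smallest Grade 2-sized fall, d = 1.6. Men: 13.0 + 1.6 = 14.6 to 14.0 + 1.6 = 15.6. Women: 11.5 + 1.6 = 13.1 to 12.5 + 1.6 = 14.1.
- Smallest Grade 3-sized fall, d = 2.1. Men: 13.0 + 2.1 = 15.1 to 14.0 + 2.1 = 16.1. Women: 11.5 + 2.1 = 13.6 to 12.5 + 2.1 = 14.6.
- Smallest Grade 4-sized fall, d = 5.1. Men: 13.0 + 5.1 = 18.1 to 14.0 + 5.1 = 19.1. Women: 11.5 + 5.1 = 16.6 to 12.5 + 5.1 = 17.6.

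**Step 2: in-range examples.**

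- Man, 17.0 to 14.4: the fall is 17.0 - 14.4 = 2.6, Grade 3 on the change row. Since 14.4 exceeds 14.0, the value is in range at every assumed LLN, so it is ungraded under Appendix 3 and normal under 3.5.8.
- Woman, 14.5 to 12.3: the fall is 14.5 - 12.3 = 2.2, Grade 3 on the change row. It is ungraded whenever the LLN is 12.3 or lower.

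**Step 3: out-of-range examples.**

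- Man, 15.0 to 12.8: 12.8 is below every assumed LLN. By value it is Grade 1 (band 12.5-13.5). By change, 15.0 - 12.8 = 2.2, it is Grade 3.
- Woman, 13.0 to 10.9: 10.9 is below every assumed LLN. By value it is Grade 2 (band 9.5-10.9). By change, 13.0 - 10.9 = 2.1, it is Grade 3.

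The double grade arises because two rows run side by side with no order of precedence. The range condition does not cause it.

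**Step 4: what follows.** An in-range fall is absent from the SAP grade summary and the Grade 2-or-higher listing, and on grade alone it triggers neither repeat testing nor Grade 3 adverse event entry. It also does not count toward the pause criterion. That criterion needs at least two Grade 3 or higher laboratory toxicities of one kind in a cohort, judged potentially related to the vaccine. Two men in one cohort each going from 15.0 to 12.8 could be tabulated as two Grade 1 results or as two Grade 3 results of one kind.

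**The case against.** Five points can be made for the plan.

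- **The laboratory manual may settle it.** Appendix 3 delegates study-specific grades to a manual that is not among the documents, and table footnotes call the tabulated values guidelines. This stands as a limit on the finding. The footnotes concern institutional ranges, however, and do not rank the rows. Even if the manual resolves the matter, the protocol and SAP texts would still need to agree with it.
- **The range condition has a sensible use.** The change rows make any decrease Grade 1, and every Grade 1 result needs an investigator's judgment of clinical significance. Without the condition, trivial fluctuation would be graded. This stands, and it is why the proposed row starts at Grade 2.
- **The wording is not uniform.** The word only is in Appendix 3 alone, and the automatic normal classification is in 3.5.8 alone. The conflict comes from reading the sections together.
- **The triggers are thresholds.** A result that meets a Grade 3 row can be read as satisfying a Grade 3-or-higher rule, whatever the other row says. That is a reasonable reading, but neither document states it, and it does not settle what the grade table shows.
- **In-range falls remain visible.** SAP 9.2 lists all laboratory results and summarizes changes from baseline. Protocol 3.6.5.2 promises absolute and change values according to the toxicity table. Under 3.5.8 a clinically significant value can be an adverse event below Grade 3, and 3.4.2.2 allows an unscheduled committee meeting for other safety concerns.

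A reader might infer that the change rows are disabled, or that the falls are hidden from the report. The documents do not support either reading: the change rows still apply once a value is out of range, and the falls appear in the listings and continuous summaries. Nor do the documents support inferring that one ungraded fall defeats the pause rule, given its further conditions.

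**Conclusion.** The finding holds in a limited form. As written, the protocol leaves a Grade 3-sized hemoglobin fall ungraded if it ends inside the laboratory's range. Under the assumed lower limits, this is possible from baselines of at least 15.1-16.1 g/dL in men and 13.6-14.6 g/dL in women. Those thresholds move one for one with the true limit. A Grade 4-sized fall could stay in range only from much higher baselines.

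Separately, an out-of-range hemoglobin can carry two grades up to two steps apart in the examples worked, with no rule for which is reported.

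The documents give no distribution of baseline hemoglobin or of falls, so the number of subjects affected cannot be estimated. The consequence is incomplete and ambiguous grading for one parameter within a primary safety endpoint. The underlying measurements are not lost. A correction is worth making because a stated rule, and not merely missing detail, keeps these falls out of the graded output. The laboratory manual could narrow the problem.

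**What to change.** **SAP 9.2.** Tabulate the hemoglobin change-from-baseline grade, Grade 2 and above, as its own row beside the absolute-value grade. Derive it for every subject regardless of the normal range, using the safety Baseline of SAP section 5 (the latest available measurement before the first vaccination, repeats and unscheduled results included). Label it as a reporting derivation, so that it does not of itself set any clinical trigger.

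**Protocol.** Reconcile sections 3.5.7.4, 3.5.8 and 6.3 with the change rows of Table 6-4 and with the laboratory manual. State whether the range condition applies to those rows, and which grade is reported when the value and change rows both apply. Which grade governs repeat testing, adverse event entry and the pause rule is for the sponsor to decide and write down.

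**Cost.** One derived row in the SAP laboratory table, a clarifying sentence in Appendix 3 with matching wording in the two body sections, and a check of the manual. No new data are needed. The downside is a few more graded hemoglobin results to review.

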**Table 6-3** **Tables for Clinical Abnormalities**

Local Reaction to Injectable Product	Mild (Grade 1)	Moderate (Grade 2)	Severe (Grade 3)	Potentially Life Threatening (Grade 4)
Pain	Does not interfere with activity	Repeated use of non-narcotic pain reliever > 24 hours or interferes with activity	Any use of narcotic pain reliever or prevents daily activity	ER visit or hospitalization
Tenderness	Mild discomfort to touch	Discomfort with movement	Significant discomfort at rest	ER visit or hospitalization
Erythema/Redness*	2.5 – 5 cm	5.1 – 10 cm	> 10 cm	Necrosis or exfoliative dermatitis
Induration/Swelling**	2.5 – 5 cm and does not interfere with activity	5.1 – 10 cm or interferes with activity	> 10 cm or prevents daily activity	Necrosis

Abbreviation: ER, emergency room.

\* In addition to grading the measured local reaction at the greatest single diameter, the measurement should be recorded as a continuous variable.

\*\* Induration/swelling should be evaluated and graded using the functional scale as well as the actual measurement.

Source: Guidance for industry – Toxicity grading scale for healthy adult and adolescent volunteers enrolled in preventative vaccine clinical trials; Tables for clinical abnormalities ([CBER 2007](#)).

Vital Signs *	Mild (Grade 1)	Moderate (Grade 2)	Severe (Grade 3)	Potentially Life Threatening (Grade 4)
Tachycardia (beats per minute)	101 – 115	116 – 130	> 130	ER visit or hospitalization for arrhythmia
Bradycardia (beats per minute)**	50 – 54	45 – 49	< 45	ER visit or hospitalization for arrhythmia
Hypertension (systolic) (mm Hg)	141 – 150	151 – 155	> 155	ER visit or hospitalization for malignant hypertension
Hypertension (diastolic) (mm Hg)	91 – 95	96 – 100	> 100	ER visit or hospitalization for malignant hypertension
Hypotension (systolic) (mm Hg)	85 – 89	80 – 84	< 80	ER visit or hospitalization for hypotensive shock
Respiratory rate (breaths per minute)	17 – 20	21 – 25	> 25	Intubation

Abbreviation: ER, emergency room.

Note that fever is classified under systemic reactions for grading purposes.

\* Subject should be at rest for all vital sign measurements.

\*\* When resting heart rate is between 60 – 100 beats per minute. Use clinical judgment when characterizing bradycardia among some healthy subject populations, for example, conditioned athletes.

Source: Guidance for industry – Toxicity grading scale for healthy adult and adolescent volunteers enrolled in preventative vaccine clinical trials; Tables for clinical abnormalities ([CBER 2007](#)).

Systemic (General)	Mild (Grade 1)	Moderate (Grade 2)	Severe (Grade 3)	Potentially Life Threatening (Grade 4)
Fever (°C) * (°F) *	38.0 – 38.4 100.4 – 101.1	38.5 – 38.9 101.2 – 102.0	39.0 – 40 102.1 – 104	> 40 > 104
Nausea/vomiting	No interference with activity or 1 to 2 episodes/ 24 hours	Some interference with activity or > 2 episodes/ 24 hours	Prevents daily activity, requires outpatient IV hydration	ER visit or hospitalization for hypotensive shock
Diarrhea	2 – 3 loose stools or < 400 g/ 24 hours	4 – 5 stools or 400 – 800 g/ 24 hours	6 or more watery stools or > 800 g/ 24 hours or requires outpatient IV hydration	ER visit or hospitalization
Headache	No interference with activity	Repeated use of non-narcotic pain reliever > 24 hours or some interference with activity	Significant; any use of narcotic pain reliever or prevents daily activity	ER visit or hospitalization
Fatigue/Malaise (unusual tiredness)	No interference with activity	Some interference with activity	Significant; prevents daily activity	ER visit or hospitalization
Generalized myalgia (muscle ache or pain)	No interference with activity	Some interference with activity	Significant; prevents daily activity	ER visit or hospitalization
Generalized arthralgia (joint ache or pain)	No interference with activity	Some interference with activity not requiring medical intervention	Prevents daily activity and requires medical intervention	ER visit or hospitalization

Abbreviations: ER, emergency room; IV, intravenous.

\* Oral temperature; no recent hot or cold beverages or smoking.

Sources: Guidance for industry – Toxicity grading scale for healthy adult and adolescent volunteers enrolled in preventative vaccine clinical trials; Tables for clinical abnormalities ([CBER 2007](#)), Division of AIDS (DAIDS) Grading the Severity of Adult and Pediatric Adverse Events ([DAIDS 2014](#)).

**Table 6-4** **Tables for Laboratory Abnormalities**

Serum Chemistry*	Mild (Grade 1)	Moderate (Grade 2)	Severe (Grade 3)	Potentially Life Threatening (Grade 4)**
Sodium – hyponatremia (mEq/L)	132 – 134	130 – 131	125 – 129	< 125
Sodium – hypernatremia (mEq/L)	144 – 145	146 – 147	148 – 150	> 150
Potassium – hyperkalemia (mEq/L)	5.1 – 5.2	5.3 – 5.4	5.5 – 5.6	> 5.6
Potassium – hypokalemia (mEq/L)	3.5 – 3.6	3.3 – 3.4	3.1 – 3.2	< 3.1
Glucose – hypoglycemia (mg/dL)	65 – 69	55 – 64	45 – 54	< 45
Glucose – hyperglycemia Random (mg/dL)	110 – 125	126 – 200	> 200	Insulin requirements or hyperosmolar coma
Blood urea nitrogen (mg/dL)	23 – 26	27 – 31	> 31	Requires dialysis
Creatinine (mg/dL)	1.5 – 1.7	1.8 – 2.0	2.1 – 2.5	> 2.5 or requires dialysis
Calcium – hypocalcemia (mg/dL)	8.0 – 8.4	7.5 – 7.9	7.0 – 7.4	< 7.0
Calcium – hypercalcemia (mg/dL)	10.5 – 11.0	11.1 – 11.5	11.6 – 12.0	> 12.0
Albumin – hypoalbuminemia (g/dL)	2.8 – 3.1	2.5 – 2.7	< 2.5	–
Total Protein – hypoproteinemia (g/dL)	5.5 – 6.0	5.0 – 5.4	< 5.0	–
Alkaline phosphate; increase by factor	1.1 – 2.0 × ULN	2.1 – 3.0 × ULN	3.1 – 10 × ULN	> 10 × ULN
Liver function tests –ALT and AST; increase by factor	1.1 – 2.5 × ULN	2.6 – 5.0 × ULN	5.1 – 10 × ULN	> 10 × ULN
Bilirubin – when accompanied by any increase in liver function test; increase by factor	1.1 – 1.25 × ULN	1.26 – 1.5 × ULN	1.51 – 1.75 × ULN	> 1.75 × ULN
Bilirubin – when liver function test is normal; increase by factor	1.1 – 1.5 × ULN	1.6 – 2.0 × ULN	2.0 – 3.0 × ULN	> 3.0 × ULN
Pancreatic enzymes – amylase and lipase	1.1 – 1.5 × ULN	1.6 – 2.0 × ULN	2.1 – 5.0 × ULN	> 5.0 × ULN

Abbreviations: ALT, alanine aminotransferase; AST, aspartate aminotransferase; ULN, upper limit of the normal range.

\* The laboratory values provided in the tables serve as guidelines and are dependent upon institutional normal parameters. Institutional normal reference ranges should be provided to demonstrate that they are appropriate.

\*\* The clinical signs or symptoms associated with laboratory abnormalities might result in characterization of the laboratory abnormalities as potentially life threatening (Grade 4). For example, a low sodium value that falls within a Grade 3 parameter (125 – 129 mEq/L) should be recorded as a Grade 4 hyponatremia event if the subject had a new seizure associated with the low sodium value.

Source: Guidance for industry – Toxicity grading scale for healthy adult and adolescent volunteers enrolled in preventative vaccine clinical trials; Tables for laboratory abnormalities (CBER 2007).

Hematology *	Mild (Grade 1)	Moderate (Grade 2)	Severe (Grade 3)	Potentially Life Threatening (Grade 4)
Hemoglobin (female) (g/dL)	11.0 – 12.0	9.5 – 10.9	8.0 – 9.4	< 8.0
Hemoglobin (female) change from Baseline value (g/dL)	Any decrease – 1.5	1.6 – 2.0	2.1 – 5.0	> 5.0
Hemoglobin (male) (g/dL)	12.5 – 13.5	10.5 – 12.4	8.5 – 10.4	< 8.5
Hemoglobin (male) change from Baseline value (g/dL)	Any decrease – 1.5	1.6 – 2.0	2.1 – 5.0	> 5.0
WBC increase (cell/mm  )	10 800 – 15 000	15 001 – 20 000	20 001 – 25 000	> 25 000
WBC decrease (cell/mm  )	2500 – 3500	1500 – 2499	1000 – 1499	< 1000
Lymphocytes decrease (cell/mm  )	750 – 1000	500 – 749	250 – 499	< 250
Neutrophils decrease (cell/mm  )	1500 – 2000	1000 – 1499	500 – 999	< 500
Eosinophils (cell/mm  )	650 – 1500	1501 – 5000	> 5000	Hypereosinophilic
Platelets decreased (cell/mm  )	125 000 – 140 000	100 000 – 124 000	25 000 – 99 000	< 25 000
PT; increase by factor	1.0 – 1.10 × ULN	1.11 – 1.20 × ULN	1.21 – 1.25 × ULN	> 1.25 × ULN
PTT; increase by factor	1.0 – 1.2 × ULN	1.21 – 1.4 × ULN	1.41 – 1.5 × ULN	> 1.5 × ULN

Abbreviations: PT, prothrombin time; PTT, partial thromboplastin time; ULN, upper limit of normal; WBC, white blood cell.

\* The laboratory values provided in the tables serve as guidelines and are dependent upon institutional normal parameters. Institutional normal reference ranges should be provided to demonstrate that they are appropriate.

Source: Guidance for industry – Toxicity grading scale for healthy adult and adolescent volunteers enrolled in preventative vaccine clinical trials; Tables for laboratory abnormalities (CBER 2007).

Urine *	Mild (Grade 1)	Moderate (Grade 2)	Severe (Grade 3)	Potentially Life Threatening (Grade 4)
Protein	Trace	1+	2+	Hospitalization or dialysis
Glucose	Trace	1+	2+	Hospitalization for hyperglycemia
Blood (microscopic) – red blood cells per high power field (rbc/hpf)	1 – 10	11 – 50	> 50 and/or gross blood	Hospitalization or packed red blood cells transfusion

\* The laboratory values provided in the tables serve as guidelines and are dependent upon institutional normal parameters. Institutional normal reference ranges should be provided to demonstrate that they are appropriate.

Source: Guidance for industry – Toxicity grading scale for healthy adult and adolescent volunteers enrolled in preventative vaccine clinical trials; Tables for laboratory abnormalities ([CBER 2007](#)).

